4. LIST OF ABBREVIATIONS AND DEFINITIONS OF TERMS

The following abbreviations and specialist terms are used in this study protocol.

Table 4: Abbreviations and Specialist Terms

Abbreviation	Definition
AE	adverse event
AESI	adverse event of special interest
BMI	body mass index
CNS	central nervous system
ECG	electrocardiogram
eCRF	electronic case report form
EOS	End of Study
FDA	Food and Drug Administration
GCP	Good Clinical Practice
ICF	informed consent form
ICH	International Council for Harmonisation of Technical Requirements for Pharmaceuticals for Human Use
IEC	independent ethics committee
IP	investigational product
IRB	institutional review board
IV	intravenous
MedDRA	Medical Dictionary for Regulatory Activities

Abbreviation	Definition
QTcF	QT corrected according to Fridericia's formula
SAE	serious adverse event
SAP	statistical analysis plan
SD	standard deviation
SPL	sound pressure level
TEAE	treatment-emergent adverse event
TMS	transcranial magnetic stimulation
UP	unanticipated problem
USM	urgent safety measure
VAS	Visual Analog Scale
VAS-A	VAS annoyance
VAS-L	VAS loudness
WOCBP	woman of childbearing potential

5. INTRODUCTION

Individuals with tinnitus hear sounds, ringing, buzzing, humming, clicking or other noises that usually originate in the auditory pathway rather than from an internal or external source. Tinnitus can be caused by either an underlying medical condition, such as noise trauma or age-related hearing loss, ear injury, or cardiovascular disease, or other causes, including medication use. Tinnitus is estimated to occur in approximately 1 in 10 adults in the US population (Bhatt et al 2016).

The presentation of tinnitus varies greatly among individuals. Most individuals with tinnitus experience subjective tinnitus, which is defined as the perception of sound(s) in the absence of a corresponding external or internal sound source. The duration of tinnitus symptoms after its initial onset is also used to classify the condition, and expert guidance defines tinnitus as acute if experienced for less than 3 months, as sub-acute after 3 months, and "chronic" for periods of 6 months or longer (Cima et al 2019). Tinnitus can also affect quality of life, and the term "bothersome" tinnitus designates cases in which the perception of the characteristic sound becomes very disturbing, and may be associated with anxiety, depression, sleep disturbances, and maladaptive psychological reactions that impede daily function (Cima 2018).

Disruption in γ -aminobutyric acid (GABA)ergic signaling affects the critical balance between excitatory and inhibitory inputs to central auditory pathways in both normal hearing and tinnitus. The GABA_A receptor is expressed in the auditory system, particularly concentrated in the cochlea, and specific receptor subunits appear associated with long-term maintenance of hair cells and neurons in the inner ear (Maison et al 2006). Reductions in auditory cortex GABA levels occur with older age and correspond to elevated pure-tone hearing thresholds in humans (Gao et al 2015). The inhibitory function of the GABA-gated chloride channel (GABA_A) receptor is also thought to be critical for auditory processing, including sound segmentation and multi-sensory integration, by modulating input/output, frequency tuning, and temporal response accuracy (Wang et al 2008).

There are currently no Food and Drug Administration (FDA)-approved pharmacological or nonpharmacological treatments for tinnitus. However, attenuation of some tinnitus symptoms has been reported with a variety of GABAergic drugs, including benzodiazepine derivatives alprazolam (Johnson et al 1993) and clonazepam (Bahmad et al 2006), and the GABA homolog gabapentin (Zapp 2001; Shulman et al 2002; Bauer and Brozoski 2006) under select circumstances. Considering the inconsistent effects of conventional GABAergic drugs, agents that significantly potentiate extrasynaptic GABA_A receptors may offer unique benefit in the management of tinnitus relative to drugs with low affinity at extrasynaptic GABA_A receptors (Witkin et al 2022). Therefore, the investigation of the use of brexanolone, a positive allosteric modulator of synaptic and extra-synaptic GABA_A receptors, in the treatment of tinnitus is supported by both nonclinical and clinical data.

5.1. Study Rationale

Brexanolone is a potent positive allosteric modulator of synaptic and extra-synaptic $GABA_A$ receptors and has potential to enhance both phasic and tonic inhibition in the brain. Brexanolone was formulated to be chemically identical to allopregnanolone, a metabolite of progesterone and endogenous neuroactive steroid.

Tonic conductance of extrasynaptic GABA_A receptors is considered critical to producing shunting inhibition that regulates neuronal network excitability. By this rationale, it has been proposed that neurosteroids, including brexanolone, may show unique potential in the management of tinnitus when compared to drugs with selective affinity for synaptic GABA_A receptors.

5.2. Effects of GABA_A Receptors in the Auditory Pathway

GABA is an amino acid that functions as an important inhibitory neurotransmitter for the CNS (Watanabe et al 2002). Disruption in GABAergic signaling affects the critical balance between excitatory and inhibitory inputs to central auditory pathways in both normal hearing and tinnitus. The GABAA receptor is expressed in the auditory system, particularly concentrated in the cochlea, and specific receptor subunits appear associated with long-term maintenance of hair cells and neurons in the inner ear (Maison et al 2006). Reductions in auditory cortex GABA levels occur with older age and correspond to elevated pure-tone hearing thresholds in humans (Gao et al 2015). The inhibitory function of the GABAA receptor is also thought to be critical for auditory processing, including sound segmentation and multi-sensory integration, by modulating input/output, frequency tuning, and temporal response accuracy (Wang et al 2008).

Loss of inhibition in the GABA pathway and specific potassium pathways plays a role in the pathology of tinnitus in animal models (Yang et al 2011; Li et al 2013). Studies in humans support the findings in animal models. A significant decrease in GABA_A receptor density in the medial temporal cortex in patients with severe disabling tinnitus and hearing loss was observed with single-photon emission computed tomography (Sedley et al 2015). An investigation using two-dimensional J-resolved spectroscopy identified lower glutamate and GABA concentrations in auditory cortices of tinnitus patients, as well as a correlation between glutamate concentration and perceived tinnitus loudness, suggesting the influence of excessive excitatory activity (Isler et al 2022).

5.3. Support for Use of Brexanolone in Tinnitus

Although no medications are approved for use in tinnitus management, and current guidelines discourage their use (Tunkel et al 2014), attenuation of some tinnitus symptoms has been reported with a variety of GABAergic drugs, including benzodiazepine derivatives alprazolam (Johnson et al 1993) and clonazepam (Bahmad et al 2006), and the GABA homolog gabapentin (Zapp 2001; Shulman et al 2002; Bauer and Brozoski 2006) under select circumstances.

Considering the inconsistent results for conventional GABAergic drugs in tinnitus, agents that significantly potentiate extrasynaptic GABA_A receptors may offer unique benefit in the management of tinnitus relative to drugs with low affinity at extrasynaptic GABA_A receptors (Witkin et al 2022). The GABAergic compound gaboxadol, which selectively activates extrasynaptic GABA_A receptors, has successfully ameliorated tinnitus in animal studies (reviewed in Richardson et al 2012). This selective activation of extrasynaptic GABA_A receptors by low concentrations of gaboxadol reduces spontaneous and evoked firing rates of sensory thalamic neurons involved in tinnitus. Such reductions in excitability of auditory thalamus/medial geniculate body (MGB) neurons following activation of extrasynaptic GABA_A receptors in tinnitus could prove advantageous in reducing the transmission of hyperexcitability to the auditory cortex (Herd et al 2009).

While brexanolone is approved for the treatment of postpartum depression (PPD), its efficacy has also been examined in the management of super-refractory status epilepticus (SRSE). SRSE is a life-threatening form of status epilepticus that recurs despite 24 hours or more of continuous intravenous (IV) administration of anesthetic third-line agents. In a Phase 2, open-label study using a targeted burst-suppression regimen (the STATUS study), brexanolone was associated with a statistically significant increase in quantitative EEG suppression ratio (qSR) during the initial 1-hour loading infusion (which targeted a plasma concentration of 150 nM). Moreover, initial qSR increase was positively correlated with brexanolone plasma concentrations over first 9 hours of infusion (maintenance infusion of 86 mcg/kg/hour). These findings support the potential of brexanolone to enhance neural inhibition in presence of aberrant excitatory activity with brief exposure (Rosenthal et al 2015a; Rosenthal et al 2015b).

Based on the data for GABAergic compounds in tinnitus, suppression of aberrant excitatory activity by brexanolone in SRSE, and the potential role of GABA in the pathogenesis of this disorder, brexanolone, a positive allosteric modulator of synaptic and extra-synaptic GABAA receptors, is being evaluated in the treatment of patients with tinnitus.

5.4. Dose Justification

Brexanolone, administered as a 60-hour infusion, is approved for the treatment of postpartum depression (PPD) in patients 15 years and older with a maintenance infusion rate of 90 mcg/kg/hour for 28 hours. In the present study, a 5-hour duration infusion given at 90 mcg/kg/hour following a period of up-titration in otherwise healthy participants with tinnitus is thought to allow adequate time to approach steady-state levels of brexanolone and anticipated to rapidly achieve plasma concentrations of brexanolone in the range experienced during therapy for PPD and during a clinical study for burst suppression in patients with SRSE (Section 5.3). Moreover, 90 mcg/kg/hour given as a short-term infusion (ie, 4 hours) was generally well-tolerated in the brexanolone ADME/mass balance study (547-CLP-101).

6. STUDY OBJECTIVES AND ENDPOINTS

Objectives	Endpoints
Primary	
To evaluate the safety and tolerability of brexanolone	Incidence of treatment-emergent adverse events (TEAEs)
Secondary	
To assess subjective tinnitus perception during brexanolone infusion based on Visual Analog Scales (VAS)	 Change from baseline to Hour 6 of infusion in VAS loudness (VAS-L) ratings Change from baseline to Hour 6 of infusion in VAS annoyance (VAS-A) ratings
To assess subjective tinnitus perception after brexanolone infusion based on VAS	 Change from baseline to post-infusion in VAS-L ratings measured via daily diary over multiple days
	 Change from baseline to post-infusion in VAS-A ratings measured via daily diary over multiple days
1	I  
_	
	Change from baseline in vital signs, electrocardiogram (ECG), and clinical laboratory parameters

[figure not shown]

7. INVESTIGATIONAL PLAN

7.1. Overall Study Design

This is an open-label study to evaluate the safety, tolerability, , and efficacy of brexanolone in adults with tinnitus following a single 6-hour continuous IV infusion. The study design is presented in Figure 2.

Figure 2: Study Design

This study includes a Screening Period of up to 28 days, a 1-day Treatment Period, and a 6-day Follow-up Period. After providing informed consent, participants will undergo screening assessments as outlined in Table 2 to determine eligibility.

Screening Period:

The Screening Period begins with the signing of the informed consent form (ICF). Eligible participants will complete additional eligibility and baseline assessments as specified in the Schedule of Assessments (Table 2).

Starting 7 days before administration of investigational product (IP) (Day -7), participants will have twice daily remote predose assessments as indicated in Table 2. Participants will receive training on how to perform all remote assessments during Screening. The participant will be contacted by the site on Day -7 through Day -1 to remind them to begin remote assessments. Assessments will be performed remotely by the participant on Day -7 through Day -1. Ratings for both VAS-L and VAS-A will be done twice daily, once each in the morning and evening.

Participants will be excluded from dosing if they do not successfully perform at least 10 of the 14 remote VAS assessments.

Clinical Protocol 547-TRM-201, Version 3.0

Treatment Period:

A continuous, 6-hour IV infusion of IP will be administered at the Clinic Treatment Visit on Day 1. Assessments will be performed as indicated in Table 3.

The participant will spend approximately 9 hours in the clinic on Day 1: 1 hour for setup of IV pump and assessments performed prior to administration of IP, 6 hours for the IP infusion, and 2 hours for safety observation at the conclusion of the IP infusion. At the discretion of the investigator, participants may stay in the clinic overnight after the end of infusion.

Due to the risk of excessive sedation and sudden loss of consciousness, for the duration of the infusion, participants will be monitored for hypoxia using continuous pulse oximetry equipped with an alarm and will be assessed for excessive sedation by a healthcare provider. If excessive sedation occurs at any time during the infusion, the infusion will be stopped until the symptoms resolve. The infusion may be resumed at the same or lower dose per protocol guidance. The infusion will be immediately stopped if pulse oximetry reveals hypoxia, specifically if this occurs in the context of excessive sedation or sudden loss of consciousness. After an episode of confirmed hypoxia, the infusion should not be resumed.

For lactating subjects, the investigator and subject should weigh the developmental and health benefits of breastfeeding during the infusion against any potential adverse effects on the breastfed child from brexanolone or from the underlying maternal condition. Subjects may continue to breastfeed or express milk to feed their infant during the infusion if the benefit is deemed to outweigh the risk. During the study, a qualified lactation consultant will be made available to subjects upon request.

In this study, excessive sedation, loss of consciousness, and any sedation-related AE that leads to dose reduction, interruption, or termination will be recorded as an adverse event of special interest (AESI).

A fall precaution protocol must be in place for the duration of the brexanolone infusion.

At the conclusion of the IP infusion, if deemed medically appropriate by the investigator, participants will be released from the clinic after the 2-hour safety observation period and completion of assessments. Participants will be cautioned against engaging in potentially hazardous activities requiring mental alertness, including driving, until any sedative effects have dissipated. A designated companion must drive the participant when they are discharged from the clinic.

Follow-Up Period:

Assessments for the Follow-up Period will be performed as indicated in Table 3. The participant will be contacted by the site on Day 2 through Day 6 to remind them to begin remote assessments. Follow-up assessments will be conducted remotely on Day 2 through Day 6. Ratings for both VAS-L and VAS-A will be done twice daily, once each in the morning and evening.

Participants will return to the clinic approximately 6 days after the last dose of IP (Day 7 ± 1 day) for efficacy and safety monitoring at the EOS Visit. The EOS Visit will also be conducted at the time of study discontinuation if this occurs at any time before Day 7 ± 1 day (see Section 8.4.2).

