This study includes a Screening Period of up to 28 days, a 1-day Treatment Period, and a 6-day Follow-up Period. After providing informed consent, participants will undergo screening assessments as outlined in Table 2 to determine eligibility.

Screening Period:

The Screening Period begins with the signing of the informed consent form (ICF). Eligible participants will complete additional eligibility and baseline assessments as specified in the Schedule of Assessments (Table 2).

Starting 7 days before administration of investigational product (IP) (Day -7), participants will have twice daily remote predose assessments as indicated in Table 2. Participants will receive training on how to perform all remote assessments during Screening. The participant will be contacted by the site on Day -7 through Day -1 to remind them to begin remote assessments. Assessments will be performed remotely by the participant on Day -7 through Day -1. Ratings for both VAS-L and VAS-A will be done twice daily, once each in the morning and evening.

Participants will be excluded from dosing if they do not successfully perform at least 10 of the 14 remote VAS assessments.

Treatment Period:

A continuous, 6-hour IV infusion of IP will be administered at the Clinic Treatment Visit on Day 1. Assessments will be performed as indicated in Table 3.

The participant will spend approximately 9 hours in the clinic on Day 1: 1 hour for setup of IV pump and assessments performed prior to administration of IP, 6 hours for the IP infusion, and 2 hours for safety observation at the conclusion of the IP infusion. At the discretion of the investigator, participants may stay in the clinic overnight after the end of infusion.

Due to the risk of excessive sedation and sudden loss of consciousness, for the duration of the infusion, participants will be monitored for hypoxia using continuous pulse oximetry equipped with an alarm and will be assessed for excessive sedation by a healthcare provider. If excessive sedation occurs at any time during the infusion, the infusion will be stopped until the symptoms resolve. The infusion may be resumed at the same or lower dose per protocol guidance. The infusion will be immediately stopped if pulse oximetry reveals hypoxia,

specifically if this occurs in the context of excessive sedation or sudden loss of consciousness. After an episode of confirmed hypoxia, the infusion should not be resumed.

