7.4. Dose Escalation and Adjustment Criteria

occurs at any time during the infusion, the infusion will be stopped until the symptoms resolve. The infusion may be resumed at the same or lower dose per protocol guidance. The infusion will be immediately stopped if pulse oximetry reveals
hypoxia. After an episode of confirmed hypoxia, the infusion should not be resumed.
If other intolerable AEs occur, the infusion will be stopped until the symptoms resolve. The

infusion may be resumed at the same or lower dose as clinically appropriate.

For participants who do not tolerate the 90 mcg/kg/hour dose for reasons other than hypoxia, a reduction to 60 mcg/kg/hour should be considered. No reductions below 60 mcg/kg/hour are permitted.

Any sedation-related AEs that lead to dose interruption, termination, or reduction should be recorded as AESIs, and should be reported in an expedited manner as outlined in Section 12.2.3.

A plasma sample for should be drawn during the time when the pump is stopped.

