10.5. Investigational Product Administration

Participants will receive a 6-hour continuous IV infusion of brexanolone on Day 1.

The specific infusion dose of IP will be calculated based on weight (obtained at Screening) for each participant and administered according to the dose regimen in Table 5.

Table 5: Infusion Rate

Time point	Day 1	Day 1	Day 1
	0 to 0.5 hours	0.5 to 1 hour	1 to 6 hours
Dose	30 mcg/kg/hour	60 mcg/kg/hour	90 mcg/kg/hour ^a

A reduction in dosage to 60 mcg/kg/hour should be considered for participants who do not tolerate 90 mcg/kg/hour. No reductions below 60 mcg/kg/hour are permitted.

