12.1.7. Continuous Pulse Oximetry

Subjects will be monitored during the infusion for hypoxia using continuous pulse oximetry equipped with an alarm. Oxygen saturation should be recorded prior to dose escalation at 0.5 hour and 1 hour. Otherwise, it need only be recorded in the event of hypoxia, in which case,

the event is to be recorded as an AE. The infusion will be immediately stopped if pulse oximetry reveals hypoxia. After an episode of hypoxia, the infusion should not be resumed.

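### The hypoxia stop rule is worded inconsistently: the Synopsis and 7.1 attach a sedation or loss-of-consciousness phrase that 7.4, 12.1.7 and SAP 4.5 do not carry.

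*Protocol*

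**What the plan says.** The Treatment Period text of Protocol 7.1 calls for the infusion to be "immediately stopped if pulse oximetry reveals hypoxia, specifically if this occurs in the context of excessive sedation or sudden loss of consciousness". The Synopsis ends the same instruction with the same words, "specifically if this occurs in the context of excessive sedation or sudden loss of consciousness". In 7.1 the next sentence is "After an episode of confirmed hypoxia, the infusion should not be resumed", which has no sedation qualifier.

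Protocol 7.4, which covers dose adjustment, orders an immediate stop and closes that sentence at the word hypoxia: "hypoxia. After an episode of confirmed hypoxia, the infusion should not be resumed". It then limits dose reduction to intolerance of other kinds: "For participants who do not tolerate the 90 mcg/kg/hour dose for reasons other than hypoxia".

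Protocol 12.1.7, on pulse oximetry, states: "The infusion will be immediately stopped if pulse oximetry reveals hypoxia. After an episode of hypoxia, the infusion should not be resumed". SAP 4.5 restates the stop without the added phrase.

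The Amendment 1 summary of changes records the phrase as a clarification and lists only the Synopsis and Section 7.1 as the places changed.

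**The concern.** This is a stopping rule for the individual participant, in a trial whose primary objective is safety and tolerability. Protocol 7.1 sets up two forms of surveillance during the infusion: alarmed continuous oximetry, and assessment of sedation by a healthcare provider. Staff need to know whether hypoxia on oximetry is enough by itself to stop the infusion.

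If the added phrase is a condition, it is not enough under the Synopsis and 7.1. Excessive sedation already stops the infusion under 7.1, so the hypoxia sentence would add little to that stop beyond making it permanent. If the phrase is emphasis, any hypoxia stops the infusion and all sections agree. Someone working only from the Synopsis or 7.1 could take the first meaning and would not see that 7.4 and 12.1.7 say otherwise.

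**Working it through.** No arithmetic applies, because the rule contains no rate, effect size or error probability. The check sets the current statements side by side.

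| Place | Immediate stop for hypoxia | Sedation or loss-of-consciousness phrase |
|---|---|---|
| Protocol Synopsis | Yes | Yes |
| Protocol 7.1 | Yes | Yes |
| Protocol 7.4 | Yes | No |
| Protocol 12.1.7 | Yes | No |
| SAP 4.5 | Yes | No |

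Of five statements, two carry the phrase and three do not. Within the protocol the split is two against two. The opening of 7.4 is cut in the public copy, but its hypoxia sentence is complete.

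**Which cases differ.**
- Hypoxia with excessive sedation or loss of consciousness: every statement stops the infusion, on either reading.
- Hypoxia alone: 7.4, 12.1.7 and SAP 4.5 stop the infusion. The Synopsis and 7.1 stop it if the phrase is emphasis. If it is a condition, their hypoxia sentence does not order a stop.

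The inconsistency is therefore confined to isolated hypoxia.

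**Support for the condition reading.** The phrase begins with the words *specifically if*. It was added by amendment, in two places only, and a reader may assume that added words change something.

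**Support for the emphasis reading.** The main clause is complete without the phrase. The paragraph in 7.1 opens by giving sedation and loss of consciousness as the reason for monitoring, so the phrase echoes that reason. The no-resume sentence that follows applies to confirmed hypoxia of any kind and presupposes a stop. Section 7.4 sets hypoxia apart from other intolerance. The amendment summary calls the change a clarification.

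**Precedence.** No visible text ranks the sections or says what the phrase is meant to do. The mismatch is between sections of the current protocol; the amendment summary serves only to show where the phrase came from.

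**Analysis.** No endpoint, analysis set or model in the SAP is defined by this wording.

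**The case against.** The strongest reply is that the sections can all be obeyed together. Section 7.1 does not say *only if*, and it nowhere permits the infusion to continue during isolated hypoxia. A site that stops for any hypoxia, as 7.4 and 12.1.7 require, complies with every section on either reading. Harm would need staff to adopt the condition reading and disregard the two sections most directly concerned with dose adjustment and oximetry. It would also need isolated hypoxia to occur, and the documents give no rate for it. The setting is small: SAP Section 12 expects about 10 dosed participants, and the Synopsis gives 1 to 2 sites.

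Most of this stands. It lowers the severity and removes any claim about dose. It does not remove the mismatch, because staff still have to reconcile four protocol statements to learn whether hypoxia alone stops the infusion. The no-resume sentence in 7.1 helps the emphasis reading without settling it: it bars a restart and does not itself order a stop.

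A reader might infer three stronger points that the documents do not support:

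- *That 7.1 allows dosing to continue through isolated hypoxia.* It contains no such permission, and 7.4 and 12.1.7 forbid it.
- *That a participant could receive a large further share of the planned dose after hypoxia.* This assumes that staff ignore two explicit stop rules and an alarm and run on to Hour 6. Nothing in the documents supports that chain of events.
- *That hypoxia lacks a needed definition of confirmed.* Section 12.1.7 does say hypoxia where other places say confirmed hypoxia, both for the bar on restarting and for recording ("Otherwise, it need only be recorded in the event of hypoxia, in which case"). But the start of 7.4 is cut, and 12.1.8 and 12.1.9 are not visible, so a definition may lie in removed text.

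**Conclusion.** The inconsistency is real and of moderate importance. It is a fault of wording in a participant-level safety rule, and the choice of stop rule itself is not in question. It bears only on hypoxia without excessive sedation or loss of consciousness. The number of participants affected cannot be estimated, and no consequence for dose, sample size, error rates or analysis can be shown.

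The conclusion rests on two things: the visible text contains no statement of precedence, and the phrase admits both readings. Emphasis is the better supported reading, but the sponsor's intent is not stated.

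**What to change.** Ask the sponsor's clinical team to confirm what the phrase was meant to do, since Amendment 1 added it deliberately. If it was emphasis, delete it from the Synopsis and 7.1 so that in both places the stop sentence ends at the word hypoxia, as it already does in 12.1.7. SAP 4.5 needs no change.

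Do not bring 12.1.7 into line by inserting *confirmed*. Its bar on restarting is the strictest in the protocol, and that edit would loosen it.

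The cost is two deletions in a wording amendment, with the IRB/IEC re-approval described in Protocol 16.1. No procedure, visit or participant is added. Some infusions may be stopped for isolated desaturation, but 7.4 and 12.1.7 already require those stops.
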